5.1 Inclusion Criteria

Subjects are eligible to be included in the study only if all of the following criteria apply:

Informed Consent

- 1 Written informed consent and written informed assent and any locally required authorisation obtained from the subject and legal representative prior to any study-related procedure taking place.

The informed consent form (ICF) process is described in Appendix [A 3](#).

Age

- 2 Age 5 to 11 years (inclusive) at Visit 1 and Visit 2 (Day 1).

Type of Subject and Disease Characteristics

- 3 Documented physician diagnosed asthma, defined by the regional guidelines (ie, National Institutes of Health [NIH], GINA, American Thoracic Society [ATS], European Respiratory Society [ERS], etc), for at least 6 months prior to Visit 1. If the subject is naïve to the study site, the participant/guardian must self-report a physician diagnosis of asthma and the investigator must confirm by review of medical history with the participant/guardian.
- 4 Documented treatment with total daily dose of either low, medium, or -high-dose ICS ($\geq 100 \mu\text{g}$ fluticasone propionate dry powder inhaler [DPI] or equivalent; see [Appendix H](#)) for at least 6 months, as described in Step 2 to Step 4 of GINA guidelines ([GINA 2020](#)) with stable dose for at least 3 months prior to Visit 1.
- 5 Additional controller medication according to standard practice of care is permitted (LABA, leukotriene receptor antagonist [LTRA], long-acting muscarinic antagonist [LAMA] only) and must be documented and stable for at least 3 months prior to Visit 1.
- 6 Inclusion criterion 6 (historical or current airway reversibility) removed with version 3.0 of Clinical Study Protocol.
- 7 Pre-bronchodilator (BD) FEV₁ of $\geq 50\%$ of predicted normal value at Visit 1.
- 8 If on allergen immunotherapy, subjects must be on stable maintenance dose and schedule ≥ 1 month prior to Visit 1.
- 9 Able and willing to comply with the requirements of the protocol.
- 10 Acceptable inhaler and spirometry techniques during screening/run-in period as assessed by the Investigator.

Weight

- 11 Body weight \geq 16 kg at Visit 1 and Visit 2 (Day 1).
- 12 Inclusion criterion 12 (Body mass index for age and percentiles) removed with version 4.0 of Clinical Study Protocol.

Sex

- 13 Male or female.

Reproduction

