8 STUDY ASSESSMENTS AND PROCEDURES

- Study procedures and their timing are summarised in the SoA ([Table 1](#)). Protocol waivers or exemptions are not allowed.
- Immediate safety concerns should be discussed with the IQVIA Global Therapeutic Medical Adviser immediately upon occurrence or awareness to determine if the subject should continue or discontinue in the study.
- Adherence to the study design requirements, including those specified in the SoA, is essential and required for study conduct.
- All screening evaluations must be completed and reviewed to confirm that potential subjects meet all eligibility criteria. The Investigator will maintain a screening log to record details of all subjects screened and to confirm eligibility or record reasons for screening failure, as applicable.

Planned sampled blood volume will be compliant with recommendations relating to GCP in the conduct of clinical trials ([European Commission 2008, Howie 2011](#)); the maximum amount of blood collected, including any losses in the manoeuvre, from each subject should not exceed 3% of the total blood volume during a period of 4 weeks and should not exceed 1% at any single time during the study ([Table 7](#)). Repeat or unscheduled samples may be taken for safety reasons or for technical issues with the samples.

Table 7 Maximum Volume of Blood to be Drawn from a Subject

Subject weight (kg)	Total blood volume (mL) ^a	Maximum blood volume (mL) to be drawn at any visit	Maximum blood volume (mL) to be drawn within a 4-week period
15-20	1200-1600	12.0-16.0	36.0-48.0
21-25	1680-2000	16.8-20.0	50.4-60.0
26-30	2080-2400	20.8-24.0	62.4-72.0
31-35	2480-2800	24.8-28.0	74.4-84.0
36-40	2880-3200	28.8-32.0	86.4-96.0
41-45	3280-3600	32.8-36.0	98.4-108.0
46-50	3680-4000	36.8-40.0	110.8-120.0
51-55	4080-4400	40.8-44.0	122.4-132.0
56-60	4480-4800	44.8-48.0	134.4-144.0
61-65	4880-5200	48.8-52.0	146.4-156.0
66-70	5280-5600	52.8-56.0	158.4-168.0
71-75	5680-6000	56.8-60.0	170.4-180.0
76-80	6080-6400	60.8-64.0	182.4-192.0
81-85	6480-6800	64.8-68.0	194.4-204.0
86-90	6880-7200	68.8-72.0	206.4-216.0
91-95	7280-7600	72.8-76.0	218.4-228.0
96-100	7680-8000	76.8-80.0	230.4-240.0

^a The total blood volume is estimated at 80 mL/kg body weight.

The total volume of blood to be drawn from each subject at each study visit is shown in [Table 8](#).

Table 8 Volume of Blood to be Drawn from Each Subject

Visit (Study day)	Sample	Sample blood volume (mL)	Visit total blood volume (mL)

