Screening	Chemistry (including β -HCG if required)	3.5	10.5
	Haematology	2.0	
	Serology (HIV)	2.5	
	Hepatitis B/Hepatitis C	2.5	
V2 (Day 1)	Chemistry	3.5	15.5
	Haematology	2.0	
	PK	2.5	
	ADA	5.0	
	IgE	2.5	
V3 (Day 3)	PK	2.5	2.5
V4 (Day 7)	PK	2.5	2.5
V5 (Day 11)	PK	2.5	2.5
V6 (Day 15)	Chemistry	3.5	8.0
	Haematology	2.0	
	PK	2.5	
V7 (Day 29)	Chemistry	3.5	15.5
	Haematology	2.0	
	PK	2.5	
	ADA	5.0	
	IgE	2.5	
V8 (Day 57)	PK	2.5	2.5
V9 (Day 85/EOS)	Chemistry	3.5	15.5
	Haematology	2.0	
	PK	2.5	
	ADA	5.0	
	IgE	2.5	
Total blood volume (mL)			75.0

Volumes exclude serum pregnancy testing (with the exception of Visit 1) and exclude any re-testing requirements. If serum pregnancy testing is needed at any other visits, then an additional 2.5 mL blood collection will be required.

[figure not shown]
ADA Anti-drug antibodies; β -HCG Beta-human chorionic gonadotrophin; EOS End of Study; HIV Human immunodeficiency virus; IgE Immunoglobulin E; PK Pharmacokinetic; V Visit.

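### Table 8's fixed blood draws exceed the protocol's own limit of 3% of blood volume per 4 weeks in the lightest eligible children: below 17.3 kg on ordinary timing, and below 19.4 kg if Visit 7 falls on Day 27 or 28

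*Protocol*

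**What the plan says.** Protocol Section 8, in the text above Table 7, commits planned sampling to two limits for each child. The volume "should not exceed 3% of the total blood volume during a period of 4 weeks", and it "should not exceed 1% at any single time during the study". Both limits apply to "the maximum amount of blood collected, including any losses in the manoeuvre". The footnote to Table 7 gives the conversion: "The total blood volume is estimated at 80 mL/kg body weight".

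Table 8 then sets out the total "volume of blood to be drawn from each subject" visit by visit:

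- screening: 10.5 mL
- V2 (Day 1): 15.5 mL
- V3, V4 and V5: 2.5 mL each
- V6 (Day 15): 8.0 mL
- V7 (Day 29): 15.5 mL
- V8: 2.5 mL
- V9: 15.5 mL

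The table does not vary by weight and shows no 4-week subtotal. Its footnote adds: "Volumes exclude serum pregnancy testing (with the exception of Visit 1) and exclude any re-testing requirements".

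Inclusion criterion 11 (Section 5.1) admits children from 16 kg. The Schedule of Activities (Section 1.3) allows screening on Day -14 to -1, V6 on Day 15 ± 1 and V7 on Day 29 ± 2. The first bullet of Section 8 says: "Protocol waivers or exemptions are not allowed".

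**The concern.** The limit scales with body weight and the schedule does not, so below some weight the two must conflict. What matters is whether that weight lies above the 16 kg floor. If it does, a site with a light child must either exceed a stated safety limit or shrink or omit a required sample, with no guidance on which. The primary pharmacokinetic samples and the ADA samples would be among the candidates.

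Table 7 makes the conflict easy to miss. It prints the 4-week limit for the 15–20 kg row as 36.0–48.0 mL. Both planned totals worked out below are under 48.0 mL, so a reader who looks at the upper figure sees no problem. The limit is a percentage of each child's own blood volume, so a 16 kg child sits near the bottom of that range.

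**Working it through.** **Plan's own figures.** Table 8 adds up: 10.5 + 15.5 + 2.5 + 2.5 + 2.5 + 8.0 + 15.5 + 2.5 + 15.5 = 75.0 mL, the printed total. The 15–20 kg row of Table 7 also reproduces: 15 × 80 × 0.03 = 36.0 mL and 20 × 80 × 0.03 = 48.0 mL.

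**Limit per child.** 0.03 × 80 = 2.4 mL/kg. At 16 kg this is 38.4 mL. The weight below which a window breaks the limit is its volume divided by 2.4.

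**Window 1, screening to V6.** 10.5 + 15.5 + (3 × 2.5) + 8.0 = 41.5 mL, and 41.5 / 2.4 = 17.29 kg.

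- At 16 kg: 41.5 − 38.4 = 3.1 mL over (8%), or 41.5 / 1280 = 3.24% of blood volume.
- At 17 kg: 41.5 − 40.8 = 0.7 mL over (2%).

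Timing: there is no Day 0, so the inclusive number of calendar days is the V6 day minus the screening day. This is 28 or fewer for screening from Day -14 if V6 is on Day 14 (14 dates), from Day -13 if V6 is on Day 15 (13 dates), and from Day -12 if V6 is on Day 16 (12 dates). That makes 14 + 13 + 12 = 39 of 3 × 14 = 42 date pairs.

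**Window 2, V2 to V7.** 15.5 + 7.5 + 8.0 + 15.5 = 46.5 mL, and 46.5 / 2.4 = 19.375 kg.

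- At 16 kg: 46.5 − 38.4 = 8.1 mL over (21%), or 46.5 / 1280 = 3.63% of blood volume.
- At 18 kg: 46.5 − 43.2 = 3.3 mL over (8%).

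Timing: Day 1 to Day 27 or 28 is 27 or 28 calendar days, so this window counts only when V7 is early. Day 1 to the nominal Day 29 is 29 calendar days. In that case V2 to V6 and V3 to V7 are 31.0 mL each, which complies at 16 kg.

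**Extreme.** Screening on Day -1 with V7 on Day 27 puts all 57.0 mL inside 28 days, over the limit below 57.0 / 2.4 = 23.75 kg. It is 1 of 14 × 5 = 70 date pairs and only a theoretical case.

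**Other reading of 4 weeks.** If 28 elapsed days are meant, window 1 fits in 41 of 42 pairs (all but Day -14 with Day 16), and window 2 already applies at the nominal Day 29. The calendar-day reading used above is the more lenient one.

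**Does correcting the 1% limit suffice?** The 15.5 mL draws at V2, V7 and V9 also exceed the single-visit limit below 15.5 / 0.8 = 19.375 kg. Trimming V2 and V7 to 12.8 mL (1% at 16 kg) gives:

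- Window 1: 10.5 + 12.8 + 7.5 + 8.0 = 38.8 mL, still 0.4 mL over. In general, 0.8w + 26.0 = 2.4w gives w = 16.25 kg.
- Window 2: 12.8 + 15.5 + 12.8 = 41.1 mL, still 2.7 mL over. In general, 1.6w + 15.5 = 2.4w gives w = 19.375 kg.

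**The case against.** The strongest reply is that this is mostly a by-product of the single-visit breach. Once V2 is cut to 1%, the ordinary-timing excess at 16 kg falls to 0.4 mL and vanishes at 16.25 kg. The rest can be avoided by not holding V7 before Day 29. That is largely right on size, but the early-V7 window still stands at 41.1 mL against 38.4 mL and nothing in the protocol rules out an early V7. The two limits have to be checked together.

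Second, some permitted schedules comply at 16 kg with full volumes, for example screening on Day -14, V6 on Day 15 and V7 on Day 29. Section 6.2.2 allows dosing to slip by 14 days, and Section 5.4 allows screening results to be reused on rescreening within 30 days. Either can move the screening draw away from V6. This stands, and 39 of 42 is a count of date pairs, not a frequency. But these are window edges or conditional cases, and the plan steers no light child towards them.

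Third, a site that draws less in order to respect a stated maximum is arguably following the protocol rather than waiving it, and tube instructions sit in a Laboratory Manual that is not available here. That is fair as far as it goes. The published table still contradicts the published limit, and the protocol names no sample to reduce. Nor does Table 8 say whether its volumes already include losses.

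Finally, few children, perhaps none, will weigh this little. At least 4 of about 14 treated children must be below 25 kg, but none need be below 19.4 kg.

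**Conclusion.** The concern holds. For children of 16 to 17.3 kg, Table 8 and the 3% limit conflict on most permitted schedules. Up to 19.4 kg they conflict whenever V7 is held on Day 27 or 28. At 16 kg the planned volume reaches 3.24% of blood volume in the first case and 3.63% in the second. The statement that planned sampling is compliant is therefore wrong for these children.

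The result rests on the protocol's 80 mL/kg, its 16 kg floor and its visit windows, with 4 weeks read as 28 calendar days, dosing not delayed and weight constant across the window. Re-tests would raise both thresholds, as would losses if Table 8 excludes them. The excess is a few millilitres in a narrow weight band and no analysis changes. It still needs correction, because it is a stated paediatric safety limit that the plan does not meet.

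**What to change.** Correct Table 8 against both limits at once. For children below about 19.4 kg, state reduced or shared planned volumes that keep every visit within 1% and every 28-day total within 3%. With the other visits unchanged, at 16 kg:

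| V2 and V7, each | Screening to V6 | V2 to V7 | Room under 38.4 mL |
|---|---|---|---|
| 11.4 mL | 26.0 + 11.4 = 37.4 mL | 15.5 + 22.8 = 38.3 mL | 0.1 mL |
| 10.5 mL | 26.0 + 10.5 = 36.5 mL | 15.5 + 21.0 = 36.5 mL | 1.9 mL |

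The 10.5 mL plan is preferable because it leaves something for losses. V9 also has to come down to 12.8 mL at 16 kg for the 1% limit.

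The laboratory should choose which tubes to shrink or share, with PK and ADA given priority. The cut is not trivial. If PK and ADA keep their 7.5 mL, chemistry, haematology and IgE must fit into 3.0 mL instead of 8.0 mL, so some sharing of serum may be needed.

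Print the planned 28-day total beside the Table 7 limit, and say how 4 weeks is counted. As a backstop for children up to about 24 kg, do not combine screening on Day -1 with V7 on Day 27. Even at 10.5 mL each, that combination totals 10.5 + 10.5 + 15.5 + 10.5 = 47.0 mL.

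The cost is revised wording in Table 8 and the Laboratory Manual, smaller or shared tubes for a few children, and the laboratory's confirmation that the volumes are enough for the assays. No extra patients are needed.

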8.1 Efficacy Assessments

Planned time points for all efficacy assessments are provided in the SoA (Table 1).

8.1.1 Spirometry

CCI

8.1.1.2 Spirometry Testing

Spirometry testing can be completed at any time during the day and within \pm 1.5 hours of the time the screening spirometry was completed. For example, if the screening spirometry is at 0800, then all spirometry testing at subsequent visits need to be completed between 0630 and 0930. On Day 1, spirometry testing will be performed before administration of IP.

[figure not shown]
The subject should wear comfortable clothing which does not restrict the chest or abdomen. The subject should rest for at least 15 minutes prior to the test and should be sitting during spirometry testing. Forced expiratory manoeuvres should be performed with the subject seated in an upright position. If this is not comfortable for the subject, standing is permitted. The same position should be used by the subject for each forced expiratory manoeuvre throughout the study. A nose-clip should be used for the manoeuvre and the head must not be tilted during manoeuvres. Mouthpieces of the same dimension and shape should be used by the subject throughout the study.

The forced expiratory manoeuvre (FEV₁) should start with a maximal inspiration and then be followed by a fast and forceful expiration that should last for at least 6 seconds. It is important to encourage the subject to continue the expiration to be fast and forceful throughout the manoeuvre. Ensure that none of the following has occurred:

- Coughing during the first second
- Glottis closure
- Leak, or
- Obstruction of the mouthpiece (by the tongue).

Multiple forced expiratory efforts (at least 3 but no more than 8) will be performed for each spirometry session and the 2 best efforts that meet ATS/ERS acceptability and reproducibility criteria will be recorded in the eCRF. The best efforts will be based on the highest FEV₁. The maximum FEV₁ of the 2 best efforts will be used for the analysis. The percentage of predicted normal value for FEV₁ will be recorded using the local spirometer at the site with predicted values derived from the appropriate reference value of choice, eg, [NHANES III 2010](#), [Quanjer et al 2012](#), etc.

CCI

CCI

8.2 Safety Assessments

Planned time points for all safety assessments are provided in the SoA ([Table 1](#)).

8.2.1 Physical Examinations

Physical examinations will be performed at timelines as specified in the SoA ([Table 1](#)).

- A complete physical examination will be performed and include assessments of the following: general appearance, respiratory, cardiovascular, abdomen, skin, head and neck (including ears, eyes, nose and throat), lymph nodes, thyroid, musculoskeletal (including spine and extremities) and neurological systems.
- A brief physical examination will include, at a minimum, assessments of the following: general appearance, respiratory, cardiovascular and abdominal systems.

See Section [8.3.5](#) for reporting AEs based on physical examinations.

8.2.1.1 Weight and Height

Weight and height will be measured in accordance with the SoA ([Table 1](#)).

The subject's weight will be recorded in kilograms, and height will be recorded in centimeters. Weight and height measurements will be performed in light clothing and with shoes off.

8.2.2 Vital Signs

Vital signs will be performed at timelines as specified in the SoA ([Table 1](#)). If required, this may be done by a study nurse at the subject's home on the Day 11 visit, if previously approved and agreed with AstraZeneca.

Vital signs (blood pressure [BP], heart rate, respiratory rate and body temperature) will be obtained in accordance with SoA.

On Day 1, vital signs will be assessed within 1 hour prior to and at 1 hour and 2 hours post-IP administration.

Vital signs will be taken prior to blood drawing, and, if possible, usual asthma controller medication.

Blood pressure and pulse measurements will be assessed in sitting position with a completely automated device. Manual techniques will be used only if an automated device is not available.

Blood pressure and pulse measurements should be preceded by at least 5 minutes of rest for the subject in a quiet setting without distractions (eg, television, cell phones).

Pulse rate will be obtained before BP, if the manual measurement technique is used.

Respiration rate will be obtained after the subject has been resting for at least 5 minutes, by counting number of breaths (ie, how many times the chest rises) for one minute.

Body temperature will be measured prior to IP administration, in accordance with local standards.

See Section [8.3.5](#) for reporting AEs based on vital signs.

8.2.3 Electrocardiograms

A 12-lead ECG will be performed at timelines as specified in the SoA ([Table 1](#)), using local site equipment.

Electrocardiograms will be taken in supine position, prior to blood draw and spirometry.

Electrocardiograms should be preceded by at least 5 minutes of rest for the subject in a quiet setting without distractions (eg, television, cell phones).

The Investigator or authorised delegate will be responsible for the overall interpretation and determination of clinical significance of any potential ECG findings. In case of discrepancy between the Investigator's interpretation and that provided by the ECG machine (if applicable), the Investigator's interpretation will take precedence and should be noted on the printout and recorded in the eCRF. A copy of the ECG will be produced, and quality checked and kept in case of further need for re-evaluation.

It is highly recommended that the same machine is used for assessment of the subject throughout the study.

The ECG data and evaluation will be recorded in the eCRF.

See Section [8.3.5](#) for reporting AEs based on vital signs.

8.2.4 Clinical Safety Laboratory Assessments

Blood and urine samples for determination of clinical chemistry, haematology and urinalysis will be taken at the visits indicated in the SoA ([Table 1](#)).

Local clinical routine procedures to reduce pain and discomfort from blood sampling in children will be followed, eg, offering topical anaesthesia, coordinated sampling to avoid repeated punctures as appropriate in accordance with ethical and instruction guidelines for paediatric blood sampling.

Additional safety samples may be collected if clinically indicated at the discretion of the Investigator. The date of collection will be recorded on the appropriate eCRF.

Instructions for sample collection, processing, storage and shipment will be provided in a separate Laboratory Manual provided to the sites.

The clinical chemistry, haematology and urinalysis will be performed at a central laboratory.

[Table 9](#) shows the laboratory variables to be measured.

Table 9 Laboratory Safety Variables

Haematology (CBC with differential)	Clinical chemistry (serum or plasma)
B-Haemoglobin (Hb)	S-Alkaline phosphatase (ALP)
B-Basophil differential count (absolute count)	S-Alanine aminotransferase (ALT)
B-Lymphocyte differential count (absolute count)	S-Aspartate aminotransferase (AST)
B-Platelet count	S-Bilirubin, total
B-Eosinophil differential count (absolute count)	S-Blood urea nitrogen
B-Monocyte differential count (absolute count)	S-Calcium, total
B-Neutrophil differential count (absolute count)	S-Chloride
White blood cell (WBC) count	S-Creatinine
	S-Creatinine kinase (CK)
Urinalysis (dipstick)^a	S-C-reactive protein (CRP)
U-Hb/Erythrocytes/Blood	S-Glucose
U-Protein/Albumin	S-beta-Human chorionic gonadotrophin (β -HCG)
U-Glucose	S-Potassium
U-Microscopy and culture as required ^b	S-Sodium
Virology screen	COVID-19 testing
Hepatitis B surface antigen (HBsAg)	Local viral rapid test
Hepatitis C virus (HCV)	
Human immunodeficiency virus (HIV)	

B Blood; CBC Complete blood count; COVID-19 Coronavirus disease 2019; S Serum; U Urine.

^aThe urine dipstick test is not only limited to blood, protein, and glucose, but also additional test analytes as defined by central laboratory.

^bUrine samples will be analysed locally with the urine dipstick test and sent to the central laboratory only for further microscopy and culture analysis when an abnormal dipstick result for any parameter is observed.

NB. In case a subject shows an AST or ALT $\geq 3 \times$ ULN together with total bilirubin (TBL) $\geq 2 \times$ ULN, please refer to [Appendix D](#) ‘Actions required in cases of increases in liver biochemistry and evaluation of Hy’s Law’ (HL), for further instructions. See Section [8.3.5](#) for reporting AEs based on laboratory values.

8.2.4.1 Pregnancy Test

The following tests will be performed for female subjects of childbearing potential (determined at the discretion of the Investigator), as specified in the SoA ([Table 1](#)).

- Serum beta-human chorionic gonadotrophin (β -HCG) at Visit 1.
- Urine pregnancy test (dipstick) at Visit 2 (treatment day) and EOS visit. A positive urine test result must be confirmed with a serum pregnancy test.

8.2.5 Other Safety Assessments

8.2.5.1 Virology

Hepatitis B surface antigen (HBsAg), hepatitis C antibody (HCAb), HIV-1 and HIV-2 antibodies will be assessed at Visit 1 only. All testing for these will be performed at a central laboratory.

Local COVID-19 viral rapid test results must be recorded in the eCRF.

Instructions for sample collection, processing, storage and shipment will be provided in a separate Laboratory Manual provided to the sites.

8.2.5.2 COVID-19 Testing

Due to the changing landscape surrounding COVID-19 testing, a local COVID-19 rapid test has become available during study conduct and is permitted for site use per the SoA ([Table 1](#)) provided:

- Test turnaround time is less than 60 minutes in order to minimise subject/caregiver time spent at site visits
- Sensitivity and specificity are at least 95%
- Test is approved by the Sponsor

After local COVID-19 viral rapid testing at V1 and V2, repeat testing may be performed at any time for a subject suspected of having COVID-19 using either viral rapid testing or testing via the central laboratory.

Local COVID-19 viral rapid test results must be recorded in the eCRF.

Instructions for sample collection, processing, storage and shipment will be provided in a separate Laboratory Manual provided to the sites.

